- The parameter estimates from the repeated measures analysis of ANCOVA based on each imputed dataset will be combined using SAS PROC MIANALYZE with MODEFFECTS statement.

A restricted maximum likelihood-based mixed model for repeated measures (MMRM) under the assumption of MAR will be also considered as sensitivity analysis to test the difference between the overall least squares mean of the treatment arms. The dependent variable of the models will be the scale scores measured at each visit. The model will include treatment arm, visit (coded using integers representing cycle number), treatment-by-visit interaction, randomization stratification factors, the baseline score

(covariate), and baseline score-by-visit interaction as the fixed effect; subject as the random effect. An empirical structure will be assumed for the variance-covariance matrix of the fixed effect parameters and an unstructured covariance matrix will be used for the random effect. The least square mean by treatment arm and the least square mean difference between treatment arms will be reported along with the corresponding 95% CI.

Patient-reported treatment satisfaction (the Satisfaction with Therapy scale of CTSQ) after cycle 4 of treatment: Patient-reported treatment satisfaction are measured by the Satisfaction with Therapy (SWT) scale of the Cancer Therapy Satisfaction Questionnaire (CTSQ) and will be collected on Day 1 of Cycle 2, Cycle 5, Cycle 12 before dosing, and safety follow-up. The scale scores will be converted to range from 0-100, with a higher score associated with the best outcome on each domain. Principles for scoring are detailed in [Appendix B](#).

Patient-reported treatment satisfaction (CTSQ) after cycle 4 of treatment will be analyzed at the corresponding fixed time point using ANCOVA method. The dependent variable of the models will be the scale scores measured at each visit (**Cycle 5 Day 1, Cycle 12 Day 1 and safety follow-up**). The model will include treatment arm, randomization stratification factors and the **scale score measured at Cycle 2 Day 1**. The mean score difference with 95% CI between treatment arms will be reported. The analyses will be performed for the ITT Analysis Set.

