**Table 2-1. Schedule of Activities**

PROCEDURE	Screening a (up to 28 days before randomization)	Treatment Period Cycles 1 to 12							Safety FU (30 [+3] days after last dose)	LTFU b (every 28 ± 7 days)	Notes
		Day 1	2	8	9	15	16	22			
PHARMACODYNAMIC ASSESSMENTS (ONLY FOR SUBJECTS IN OPTIONAL INTENSIVE PK/PDN SUBSTUDY)											
Cycle 1		X		X							Day 1 only: 

Predose (within 5 min before the start of infusion)

 Day 8 only: 

Predose (within 5 min before the start of infusion)

60 minutes (± 5 min) after the end of infusion

Cycle 2		X		X		X					• Predose (within 5 min before the start of infusion) • 60 min after the end of infusion (± 5 min)
Cycle 3 to 7		X									• Predose (within 5 min before the start of infusion) • 60 min after the end of infusion (± 5 min)
CLINICAL OUTCOME ASSESSMENTS – TO BE COMPLETED PRIOR TO ANY STUDY PROCEDURE											
FORTC QLQ-C30		(X)						X			Before dosing on day 1 of cycle 1, 3, 5, 7, 9, and 12
Patient-reported convenience with carfilzomib-dosing schedule single-item question		(X)							X		Before dosing on C2D1, C5D1, and C12D1 for subjects still receiving carfilzomib.
CTSQ		(X)						X			Before dosing on C2D1, C5D1, and C12D1.

Page 7 of 8

Footnotes are defined on the last page of the table.

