
compare patient-reported physical functioning and role functioning between treatment arms	
physical functioning and role functioning over time as measured by the Physical Functioning and Role Functioning scales of the European Organization for Research and Treatment of Cancer Quality-of-life Questionnaire Core 30 (EORTC QLQ-C30) over the duration of the study

compare patient-reported treatment satisfaction between treatment arms	
treatment satisfaction as measured by the Satisfaction with Therapy (SWT) scale of the Cancer Therapy Satisfaction Questionnaire (CTSQ) after cycle 4 of treatment

Exploratory

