4.2 Subgroups

The ORR, **PFS** and **OS** will be estimated for the following selected subgroups defined by the baseline data reported on CRF or from the central lab, as appropriate. When there is not a sufficient number of subjects in the subgroup, i.e., less than 5% of the whole population, relevant subgroups may be combined.

- original ISS stage at baseline (stage 1 or 2 vs stage 3)
- prior lenalidomide treatment (yes vs no)
- prior PI treatment (yes vs no)
- prior anti-CD38 exposure (yes vs no)
- prior bortezomib treatment (yes vs no)
- age (years) (<65, ≥65; 18 - <65, 65 - <75, ≥75)
- region (Europe vs Non-Europe)
- baseline creatinine clearance (CrCl, mL/min) (<50, ≥50)
- number of prior therapies (1 vs >1; 1 vs 2 vs >2)
- cytogenetic risk measured by FISH (high-risk (t(4;14), t(14;16), deletion 17p) vs standard risk)
- bortezomib refractory status (yes vs no)
- lenalidomide refractory status (yes vs no)
- prior transplant (yes vs no)

5. Definitions

Baseline

The baseline value is the latest value measured on/before day 1 of the first dose of any protocol-specified therapy. If a subject doesn't receive any protocol-specified therapy, then the latest value prior to or on randomization date will be used.

For bone lesion and plasmacytoma assessment, the baseline is defined as the most recent assessment within 45 days (bone lesion) or 28 days (plasmacytoma) prior to or on the randomization date, or up to 7 days (inclusive) after initiation of the study treatment if the patient has been dosed.

Best overall response by investigator assessment

Best overall response for a subject by investigator assessment is the best post baseline confirmed response by the analysis trigger date based on the responses by visit collected on myeloma response assessment CRF. The response assessments done after confirmed disease progression or initiation of new anti-myeloma therapy will be excluded from the analysis of primary endpoint.

Best overall response by IRC assessment

Best overall response for a subject by IRC as collected on IRC Evaluation CRF. Details of the IRC will be described in the IRC charter.

Cytogenetic Risk group as determined by Fluorescent in Situ Hybridization (FISH)

Cytogenetic risk group is defined based on the central laboratory FISH analytes t(4;14), t(14;16) and deletion 17p regardless of any other FISH analyte test results.

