9.1 General Considerations

Where applicable, descriptive statistics will be provided. For continuous variables, the number of subjects with non-missing data (n), mean, standard deviation (STD), median, minimum, and maximum will be presented. For categorical variables, the frequency (n) and percentage will be summarized in each category. The denominator for percentages is the number of subjects in the analysis set of interest for the summary. The binomial proportions and the corresponding 95% confidence intervals (CIs) will be based on the exact distribution methods (Clopper-Pearson interval) and the treatment comparison will be based on Cochran-Mantel-Haenszel (CMH) method. Time to event endpoints will be estimated using the Kaplan-Meier (KM) method and will be summarized with the number of subjects with events or censored, and censoring reasons, KM quartiles (when estimable) and corresponding two-sided 95% CIs, KM proportions at select time points, inferential comparison between treatment arms with associated p-values, hazard ratios from stratified Cox proportional hazard (PH) model, and KM curves.

The analyses of efficacy and safety endpoints will be based on the analysis sets defined in [Section 6](#). The primary (final) analyses of the efficacy endpoints and Patient-report outcomes will use the ITT population, while the Per Protocol Set will be used for sensitivity analyses, if applicable. The analyses of the safety endpoint will be based on the safety population.

The primary analysis of ORR and PFS will be based on IRC assessed outcomes. The synthesis approach will be used to show that KRd 56 mg/m² QW preserves at least 60% of KRd 27 mg/m² BIW effect vs Rd in terms of ORR and 50% in terms of PFS. The null hypotheses for the primary and key secondary objectives (ORR, PFS, and convenience after cycle 4 of treatment) will be tested using a fixed sequence hierarchical testing procedure to control the family-wise type I error rate at 1-sided 0.025 level. The testing is ordered as follows: non-inferiority of ORR, non-inferiority of PFS, and superiority of patient-reported convenience after cycle 4 of treatment. Starting with the hypothesis of ORR, if any null hypothesis in the sequence is rejected, then the subsequent hypothesis

will be tested. Otherwise, if any hypothesis failed to be rejected, then the subsequent hypotheses will not be tested. For all other endpoints, the significance testing, if performed, will be considered descriptive.

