MRD[-]CR	
CR or better response component based on IRC assessments:
 
MRD[-]CR rate and 95% CI (Clopper Pearson method) by treatment armOR with 95% CI as a measure of treatment effect estimated by CMH method stratified by the randomization stratification factors	
Response based on investigator assessments for CR or better: Same as primary summary and analysis methodResponse based on internal computational assessments (ORCA): Same as primary summary and analysis method
MRD[-] status at 12 months from randomization	
MRD[-] rate and 95% CI (Clopper Pearson method) by treatment armOR with 95% CI as a measure of treatment effect estimated by CMH method stratified by the randomization stratification factors	
Physical functioning and role functioning (scales of EORTC QLQ-C30) over time	
Repeated measures analysis of covariance (ANCOVA) adjusting for the baseline covariates (treatment arm, randomization stratification factors, baseline score and visit) for the comparison of mean score over time between treatment arms	
Per Protocol Set: Same as primary summary and analysis methodRestricted maximum likelihood-based mixed model for repeated measures (MMRM) for the comparison of mean score over time between treatment arms
Patient-reported treatment satisfaction (the SWT scale of CTSQ) after cycle 4 of treatment	
ANCOVA at the corresponding fixed time point	

Table 9-3. Exploratory Efficacy Endpoint Summary Table

Endpoint	Primary Summary and Analysis Method	Sensitivity Analysis
Described in Section 2.1 table	Will be described in a supplemental analysis plan (SSAP) finalized before database lock	Will be described in a SSAP finalized before database lock

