The completion rate for scale score will be presented by treatment arm and by visit based on all randomized subjects (ITT Analysis Set) as well as all subjects expected to have an assessment at the scheduled visit (i.e., randomized subjects who are still alive and remaining on study treatment at the scheduled visit, subjects who **have ended all study treatment and are remaining on study for safety follow-up visit**).

In addition to descriptive analyses, the comparison of mean score over time between treatment arms will be performed using repeated measures analysis of covariance

(ANCOVA) adjusting for the baseline covariates in a multivariate model. The dependent variable of the models will be the scale scores measured at each post-baseline visit. The model will include treatment arm, randomization stratification factors, the baseline score (covariate, the scale score on cycle 1 day 1 before dosing) and visit as a repeated measure. The least square mean by treatment arm and the overall least square mean difference between treatment arms will be reported along with the corresponding 95% CI.

All the above analyses will be based on the ITT Analysis Set. A similar analysis will be performed on Per Protocol Set as a sensitivity analysis.

In the repeated measure ANCOVA, the missing scale scores will be imputed using multiple imputation (MI) method ([Rubin DB, 1976](#); [SAS Institute Inc., 2015](#)) with the assumption of missing at random (MAR). The steps are as follows.

- Assuming the missing data pattern is arbitrary, the MI will be performed by treatment group using the fully conditional specification (FCS) method with linear regression models, which is implemented with SAS 9.4's PROC MI under the FCS statement. The imputation model will include all the variables specified in ANCOVA model (treatment arm, randomization stratification factors, the baseline scale score). There are 50 imputed datasets to be generated. The seed of the pseudorandom number generator used to randomly generate imputations for the missing values is specified as seed=54321. Prior to MI, the dataset needs to be converted from a long to the wide format (one record per subject).
- Repeated measures analysis of ANCOVA will be performed on each imputed dataset generated in MI. Prior to analysis of the completed dataset, the dataset needs to be restructured into a long format.

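### The CTSQ satisfaction model adjusts for a score taken after a full cycle of randomized treatment, so it does not estimate the between-arm difference after cycle 4

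*SAP*

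**What the plan says.** The objective in SAP Section 2.1 is to "compare patient-reported treatment satisfaction between treatment arms". The matching endpoint is "treatment satisfaction as measured by the Satisfaction with Therapy (SWT) scale of the Cancer Therapy Satisfaction Questionnaire (CTSQ) after cycle 4 of treatment".

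Protocol Table 2-1 schedules CTSQ "Before dosing on C2D1, C5D1, and C12D1", and also at safety follow-up. SAP Section 9.5.2 gives the same times. Neither document has a CTSQ assessment before the first dose.

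The CTSQ model in SAP Section 9.5.2 is an ANCOVA fitted separately at C5D1, C12D1 and safety follow-up. Its terms are treatment arm, the stratification factors and the "scale score measured at Cycle 2 Day 1". The SAP version history shows that Amendment 2 put this visit in place of a baseline score. The output is a mean difference with a 95% CI. The CTSQ row of Table 9-2 reads "ANCOVA at the corresponding fixed time point" and lists no sensitivity analysis.

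Two other places in the SAP are useful for comparison:

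- Section 5 defines baseline: "The baseline value is the latest value measured on/before day 1 of the first dose of any protocol-specified therapy". The QLQ-C30 model in Section 9.5.2 follows this and uses "the baseline score (covariate, the scale score on cycle 1 day 1 before dosing".
- Patient-reported convenience is collected at the same four times as CTSQ. Its main analysis is stratified by the randomization factors only, and Cycle 2 is summarized as an outcome visit.

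Section 9.1 sets the inferential status: "For all other endpoints, the significance testing, if performed, will be considered descriptive".

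**The concern.** By C2D1 the arms have been scheduled for 3 versus 6 carfilzomib infusions (Protocol Section 7.1.1.2), and subjects know which schedule they are on (Section 7.3). A C2D1 satisfaction score can therefore already carry part of the schedule effect. Holding it fixed compares subjects with the same cycle 1 satisfaction and removes that part from the estimate.

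Readers will take the reported difference and interval as the satisfaction difference between schedules. If the arms differ in the same direction at C2D1 and later, the result is too small. If the early difference has the opposite sign, for example because of early tolerability, it is too large. If there is no early difference, it is unaffected. Protocol Section 3.1.2 reports higher odds of satisfaction with once-weekly dosing in the earlier once- versus twice-weekly trial, so a same-direction effect is plausible. The documents do not say when such an effect appears.

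**Working it through.** The plan states no sample size, SD, effect or correlation for CTSQ, so there is no figure of its own to reproduce.

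**Inputs.** From the documents: the visit times, the model terms and 230 subjects per arm. Assumed: the within-arm correlation ρ between the C2D1 score and a later score (0.3 to 0.7), the arm difference d1 at C2D1 as a share of the later difference d2 (−0.5, 0, 0.5, 1), and equal SDs at both visits. For coverage, also d2 = 0.30 SD and 200 scored subjects per arm.

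**Step 1: what the arm coefficient estimates.** With within-arm slope b of the later score on the C2D1 score,

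expected coefficient = d2 − b·d1, and b = ρ when the SDs are equal.

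Share of d2 kept = 1 − ρ·(d1/d2). For example, with ρ = 0.5 and d1 half of d2, this is 1 − 0.5 × 0.5 = 75%.

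| d1/d2 | ρ = 0.3 | ρ = 0.5 | ρ = 0.7 |
|---|---|---|---|
| −0.5 | 115% | 125% | 135% |
| 0 | 100% | 100% | 100% |
| 0.5 | 85% | 75% | 65% |
| 1 | 70% | 50% | 30% |

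A simulation with 200,000 subjects per arm, a true later difference of 5.0 points and SD 15 agrees. The adjusted estimates at ρ = 0.3 / 0.5 / 0.7 are 4.96 / 4.93 / 4.99 (d1 = 0), 4.19 / 3.77 / 3.24 (half) and 3.53 / 2.49 / 1.45 (equal). Without the C2D1 term the estimates are 4.91 to 5.05 throughout.

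**Step 2: does the reported 95% CI cover d2?** In SD units,

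SE = √[(2/n)(1 − ρ²)(1 + d1²/4)], bias = −ρ·d1.

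Take ρ = 0.6, d1 = 0.15, n = 200. Then SE = √(0.01 × 0.64 × 1.0056) = 0.080, bias = −0.09, and bias/SE = −1.12. Coverage ≈ Φ(1.96 − 1.12) − Φ(−1.96 − 1.12) = 80%.

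| d1/d2 | Coverage of d2 at ρ = 0.4 / 0.6 / 0.7 |
|---|---|
| 0 | 95 / 95 / 95% |
| 0.5 | 90 / 80 / 69% |
| 1 | 75 / 40 / 17% |

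Simulation with 8,000 trials per cell gives 0.904 / 0.800 / 0.684 and 0.747 / 0.398 / 0.177 for the last two rows, and 0.95 without the covariate.

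**Step 3: precision given up by dropping the covariate.** Ratio of unadjusted to adjusted SE = 1/√[(1 − ρ²)(1 + d1²/4)]. For d1 from 0 to 0.30 SD this is 1.08-1.09, 1.24-1.25 and 1.38-1.40 at ρ = 0.4, 0.6 and 0.7.

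For reference only, since the SAP plans no p-value here: two-sided 5% power at n = 200 is 85% without the covariate. With it, power is 90 / 96 / 99% (d1 = 0), 74 / 74 / 77% (half) and 49 / 32 / 24% (equal).

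**The case against.** The best defence is that the covariate is openly specified and is not called a baseline. Amendment 2 removed a reference to a baseline score that is never collected. The satisfaction items ask about the therapy received, so a score before the first dose would mean little. All of that is fair, but the lack of a usable pre-dose score is a reason to omit the covariate, not to use one affected by treatment.

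A second point is that the size is assumed throughout, and the worst cells need the whole effect to be present at C2D1 with a correlation of 0.7. Several satisfaction items, such as whether benefits meet expectations, may develop later. This stands: the mechanism is certain, the size is not, and there is no bias if d1 = 0.

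Third, some of the gap is partly covered. Section 9.1 provides general descriptive statistics, which could show unadjusted means by arm. Appendix B gives an item-level rule (at least 5 of 7 items). Section 8.3 mentions missing-data sensitivity analyses for quality-of-life endpoints. None of these gives an unadjusted between-arm CTSQ estimate with a CI, or says what happens to a subject with no C2D1 score.

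Fourth, conditioning on early satisfaction may lessen selection among those who still respond at C12D1 or safety follow-up. That is a real trade-off, and removing the covariate does not solve dropout. It supports stating a missing-data approach. It does not make the adjusted coefficient the between-arm difference.

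Finally, the wording about cycle 4 stands in the endpoint cell, not the objective cell. It is the same row of the table, and the reading does not change.

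**Conclusion.** The concern holds. As written, the only specified CTSQ comparison estimates the later difference among subjects with equal cycle 1 satisfaction. This equals the difference named by the objective and endpoint only if the arms do not differ at C2D1 or the two scores are uncorrelated within arm.

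Under the assumed correlations, the loss runs from none to 70% of the later difference, and an opposite-sign early effect of half its size inflates the estimate by 15-35%. These figures assume equal SDs, a common linear slope and complete scores. The coverage figures also depend on the assumed 0.30 SD effect and 200 scored subjects per arm.

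The consequence is confined to one descriptive secondary endpoint outside the testing sequence. It should be corrected, but it does not threaten the trial's main conclusions.

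**What to change.** Revise the CTSQ paragraph of SAP Section 9.5.2 and the matching row of Table 9-2:

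1. Main model at C5D1, C12D1 and safety follow-up: treatment arm and stratification factors. A pre-dose C1D1 QLQ-C30 physical or role functioning score may be added for precision. It is already collected, but its correlation with satisfaction is not known from the documents.
2. Report C2D1 as an outcome visit, by arm, as is already planned for convenience.
3. Keep the C2D1-adjusted model as a supportive analysis, labelled as the later difference given satisfaction after cycle 1.
4. State how subjects with missing CTSQ scores are handled. Multiple imputation is described only for the QLQ-C30 scales.

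No new data are needed. The price is a wider interval, by about 8-9%, 24-25% or 38-40% at correlations of 0.4, 0.6 or 0.7. A C1D1 functioning score might recover part of this. Dropout before the later visits remains a separate issue under either model.

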9.5.3 Analyses of Exploratory Efficacy Endpoint(s)

Details regarding the analyses of exploratory endpoints of COA will be provided in a SSAP.

9.6 Safety Analyses

9.6.1 Analyses of Primary Safety Endpoint(s)

Safety and tolerability will be assessed where applicable, by incidence, severity, seriousness, and changes from baseline for all relevant parameters including AEs, deaths, laboratory tests, vital signs, electrocardiogram (ECG) and left ventricular ejection fraction (assessed by echocardiogram (ECHO)). All safety analyses will be based on the Safety Analysis Set.

9.6.2 Adverse Events

The Medical Dictionary for Regulatory Activities (MedDRA) version 24.1 or later will be used to code all adverse events (AEs) to a system organ class (SOC) and a preferred

term (PT). AEs will be graded for severity using the National Cancer Institute Common Terminology Criteria for Adverse Events (NCI-CTCAE) version 5.0. The events of interest (EOI) search strategies will be based on the standardized MedDRA query (SMQ) and/or Amgen customized MedDRA query (AMQ). Incomplete AE start dates will be imputed according to the specifications described in [Appendix A](#).

The number and percentage of subjects experiencing AEs will be summarized for all treatment-emergent adverse events (TEAEs), grade 3 or higher TEAEs, serious TEAEs, treatment-related TEAEs, TEAEs leading to discontinuation of investigational product/non-investigational product, TEAEs leading to discontinuation of any study drug, TEAEs leading to dose reduction or interruption of investigational product/non-investigational product, TEAEs leading to dose reduction or interruption of any study drug, fatal TEAEs and treatment-emergent EOI. The subject incidence will be presented by treatment arm and tabulated by SOC (in alphabetical order) and/or PT (in descending order of frequency), and/or severity. If a subject experiences repeated episode of the same AE, the subject will be counted only once within each SOC and similarly counted once within each PT and the event with the highest severity grade will be used for purposes of incidence tabulations.

In addition, summaries of TEAEs and serious TEAEs occurring in at least 5% of the subjects by PT in any treatment arm will be provided in descending order of frequency.

A summary of the number of deaths and the cause of death, classified by deaths within 30 days of last dose of study drug and deaths more than 30 days after the last dose of study drug, will be provided.

